- ⁷³ lorcaserin (Belviq®) was associated with euphoria (0.2% vs < 0.1% for placebo) and is contraindicated in
- 74 patient's receiving serotonergic medications (and many psychotropics enhance serotonin function) (45). 75 Phenermine/topiramate combination (Qsymia®), at the highest approved dose, was associated with
- insomnia (11.1% vs 5.8% for placebo), depression/mood problems (7.6% vs 3.4% for placebo), and
 anxiety (7.9% vs 2.6% for placebo) (46). Additionally, one of the components of Qsymia®, topiramate, is 78
 associated with suicidality. Bupropion/naltrexone combination (Contrave®), at the highest recommended 79
 dose, was associated insomnia (9.2% vs 5.9% for placebo), anxiety (4.2% vs 2.8% for placebo), and
- irritability (2.6% vs 1.8% for placebo) (47). Moreover, there are reports of components of these latter
- medications (e.g., phentermine and bupropion) causing severe adverse psychiatric events, such as mania
- and psychosis (48-52). Taken together, these findings suggest that liraglutide 3.0 mg sc injection may be
- the least likely of these weight management medications to exacerbate psychiatric symptoms in people 84
- with BP. Indeed, GLP-1 analogues have been reported to produce enhanced well-being in patients with diabetes (53).
- 86
- Taken together these data support the hypothesis that liraglutide 3.0 mg sc injection will reduce body
 weight and improve metabolic variables in obese or overweight patients with BP without worsening 89
 psychiatric symptoms. We predict that liraglutide 3.0 mg sc injection will display greater efficacy as
- ⁹⁰ compared to placebo in decreasing body weight in patients with BP who are obese or overweight. To
- 91 prove this hypothesis, we will conduct a single-center, randomized, placebo-controlled, double-blind,
- parallel-group, 2-arm clinical trial of liraglutide 3.0 mg sc injection in 60 obese or overweight outpatients

with stable BP. We have chosen BP rather than another SMI because it is the most common SMI (more

- 94 common than schizophrenia or schizoaffective disorder) and has a particularly strong association with 95 obesity.
- 96

97 SPECIFIC OBJECTIVES:

98 **Primary Objective:**

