99 The primary objective of this study is to evaluate the efficacy of liraglutide 3.0 mg sc injection (in 100 combination with a reduced calorie diet and increased physical activity) compared with placebo for 101 reducing body weight in obese or overweight adults with stable BP, as measured by percent change in 102 body weight.

103

104 Secondary Objectives:

105 Secondary objectives are:

105	Secondary objectives	
106	- To ev	aluate the efficacy of liraglutide 3.0 mg sc injection as measured by:
107	-	Proportion of participants who have $a \ge 5\%$ loss in body weight
108	-	Body weight (kg)
109	-	BMI
110	-	Waist circumference
111	-	Fasting lipids
112	-	Fasting glucose
113	-	HgA1 _c levels
114	-	Three-Factor Eating Questionnaire (TFEQ) (54)
115	-	Binge Eating Scale (BES) (55)
116	- To ev	aluate the safety and tolerability of liraglutide 3.0 mg sc injection, using:
117	-	Mental status examinations
118	-	Young Mania Rating Scale (YMRS) (56)
119	-	Montgomery Asberg Depression Rating Scale (MADRS) (57)
120	-	Clinical Global Impressive Scale for modified Bipolar Disorder (CGI-BP) (58)
121	-	Physical examinations
122	-	Vital signs
123	-	12-lead electrocardiograms (ECG)
124	-	Clinical laboratory tests
125	-	Adverse event reports
126	-	Columbia-Suicide Severity Rating Scale (C-SSRS) (59)
127		
128	RESEARCH DESIG	GN AND METHODS
129		
130	Study hypothesis (es	s):
131		question is whether liraglutide 3.0 mg sc injection is efficacious for reducing body
132		verweight patients with BP. We hypothesize that liraglutide 3.0 mg sc injection will
133		e, and well tolerated treatment for weight loss in obese or overweight patients with
134		et that liraglutide 3.0 mg sc injection will display greater efficacy as compared to 135
	1 1 1 1 1	

- placebo in decreasing body weight in patients with BP who are overweight or obese without increasing
- 136 psychiatric adverse events. We also predict that liraglutide 3.0 mg sc injection will produce a greater

- percentage of patients who lose \geq 5% of baseline body weight, and improve BMI, waist circumference, 137
- fasting lipid and glucose levels, HgA1c levels, and measures of eating psychopathology. 138
- 139

140 **Endpoints:**

- The primary endpoint will be the percent change in body weight from Baseline (Week 0) to week 141
- 40/Early Termination (ET) (see Table 1 for a schedule of assessments). Secondary endpoints will include 142

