The power analysis for this study uses a two-sample t-test on the mean weight change from baseline to 510 week 40 (or endpoint for patients who discontinue prematurely) in the two treatment groups in the

- 511
- modified intent-to-treatment (ITT) sample. This sample will consist of all study participants who: 1) were 512 randomized, 2) received at least one study medication dosage, and 3) had at least one post-baseline 513
- efficacy assessment. We expect a 5% attrition rate from baseline to week 1. We therefore expect the
- 514 proposed sample size of 60 to give an ITT sample of 56. Using this ITT sample size, along with a
- 515 significance level of 0.05 and power of 0.80, we will be able to detect effect sizes as small as 0.76. 516
- 517
- This effect size corresponds to a 4.5 kg greater weight reduction in the liraglutide group vs. the placebo 518
- group. The 4.5 kg reduction was calculated (0.76 x 6.0) using an expected standard deviation (SD) of 6.0 519
- kg based on Wadden et al. (SD=7.0 at 56 weeks) and Astrup et al. (SD=5.6 for power analysis). This is a 520
- clinically meaningful difference, especially in this population, where many patients are taking 521
- 522 antipsychotics, which are associated with weight gain. We expect our primary analysis (longitudinal
- mixed model) to have more power due to the repeated visit data for each subject (60 subjects x 16 524 523
- treatment period visits = 960 maximum number of observations).

525 526

- **Statistical Methods** Chi-square, Fisher's Exact, Wilcoxon rank sum or two-sample t-tests will be used to examine statistical 527
- differences between the placebo and drug condition on baseline characteristics and categorical outcome 528
- measures. The primary analyses will be longitudinal data analyses (LDA) using PROC MIXED (SAS, 529
- Cary N.C. U.S.A.). LDA will model the mean change in the primary and secondary outcome measures, 530 over the treatment period, between the placebo and drug condition. LDA is advantageous because it 532
- 531 accounts for change over time, includes all data points, and adjusts for the correlation resulting from 533 repeated measures. These LDA models will include variables for treatment, time, and treatment x time

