- interaction. The statistical test for the interaction term will be the measure of a treatment effect. The 535 534 interaction term will test if the slopes of the regression lines for the liraglutide and placebo groups are 536 different. A group difference (Drug [week 40-week 0] – Placebo [week 40-week 0]) will be reported 537 which corresponds to the interaction term. For the primary outcome of percent change in body weight,
- only post-baseline data will be used in the LDA model and the difference between treatments at week 40 538
- will be reported. These mixed models will allow for random coefficients (intercept and time variable), as 539
- 540 well as an appropriate correlation structure for the error terms to account for within-subject
- correlation. The best model will be chosen using the Akaike Information Criterion-corrected 541
- (AICc). The distribution of the outcome measures will be checked for normality, and transformations will 542 be used when necessary. Also, a transformation on the time variable will be considered to optimize the 544 543
- assumed linear relationship.
- 545

- 546 Additionally, secondary endpoint analyses will be performed on all outcome measures. Using the last
- 547 observation carried forward (LOCF), baseline to endpoint change scores will be computed for each 548 measure and two-sample t-tests or Wilcoxon rank sum tests will be used to compare these changes 549 between the treatment groups.
- 550

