Randomization will be conducted by [name], the program manager for the Lindner Center of HOPE 551 Research Institute using the program: http://www.randomization.com. Block randomization (with block 552 size of six subjects) will be used to insure relatively equal patients in both the drug and placebo groups. 553 Antipsychotic medications used to treat BP are associated with weight gain and development of obesity 554 (much more so than mood stabilizers). Randomization of subjects will therefore include current 555 antipsychotic use (receiving at least one of the following: asenapine, aripiprazole, cariprazine, 556 chlorpromazine, clozapine, haloperidol, loxapine, olanzapine, paliperidone, perphenazine, quetiapine, 557 resperidone, thiothixene, trifluoperazine, or ziprasidone) as a stratifying factor. Of note, the average 558 number of medications BP patients receive is three. We expect that nearly all patients will be receiving a 559 mood stabilizer and that about 50%-66% of patients will also be receiving an antipsychotic drug. 560 Intermittent missing visits will be treated as missing at random and no special adjustment will be used. 561 The safety population will include all randomized participants with at least one post-baseline safety 562 assessment. Statistical analyses will be conducted by [name], MS. All analyses will be conducted 563 using SAS version 9.4 (Cary, N.C., U.S.A.). Hypotheses testing will be two-sided with a significance 565 564 level of $p \le 0.05$.

566

The randomization should balance all demographic and clinical characteristic variables between the two treatment groups and generally no covariates will be used in the analyses. However, if a significant baseline difference exists between treatment groups on a demographic or clinical characteristic variable, this variable will be checked for significant correlations with the outcomes of interest. If a correlation exists, then the variable will be added as a covariate to the efficacy analysis.

572 573

574 **DATA HANDLING AND RECORD KEEPING:**

All data will be compiled using case report forms (CRFs) that will be specifically designed for this
study. Trained research coordinators will complete the CRFs. Data from CRFs will be entered and stored
in electronic and secured databases at the LCOH.

578579 ETHICS:

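### The hypothesis includes no psychiatric worsening, but the plan has only two-sided difference tests for it: no margin, interval criterion or power for any psychiatric safety outcome

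*Combined protocol and SAP*

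**What the plan says.** The closing paragraph of the background, just before Specific Objectives, says the data support the hypothesis that liraglutide will reduce "weight and improve metabolic variables in obese or overweight patients with BP without worsening" psychiatric symptoms. It then predicts greater weight loss than placebo and says that to "prove this hypothesis, we will conduct a single-center, randomized, placebo-controlled, double-blind" trial. Study hypothesis (es) predicts greater efficacy than "placebo in decreasing body weight in patients with BP who are overweight or obese without increasing" psychiatric adverse events.

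Mental status, YMRS, MADRS, CGI-BP, C-SSRS and adverse events are listed under a secondary objective on safety and tolerability, and under Endpoints as safety endpoints.

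Statistical Methods offers four kinds of inference:
- For baseline characteristics and categorical outcomes: "Chi-square, Fisher's Exact, Wilcoxon rank sum or two-sample t-tests will be used to examine statistical" differences between the arms.
- For primary and secondary outcomes: a longitudinal mixed model in which the treatment-by-time interaction is the test of effect and a group difference is reported.
- For LOCF change scores on all outcome measures: "measure and two-sample t-tests or Wilcoxon rank sum tests will be used to compare these changes" between arms.
- For all of these, one standard: "Hypotheses testing will be two-sided with a significance" level of p ≤ 0.05.

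The only power statement, in Sample Size Calculation, concerns weight: "significance level of 0.05 and power of 0.80, we will be able to detect effect sizes as small as 0.76". The safety population is defined separately from the modified ITT sample, as all randomised participants with a post-baseline safety assessment.

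**The concern.** A statement that a drug does not increase harm is a claim of no important difference. It can be supported only by showing that the data exclude an increase of some stated size. A two-sided difference test does not do that. When it rejects, it shows a difference; when it does not, it leaves open everything inside the confidence interval. In a trial sized for a large effect on weight, that interval may be wide for psychiatric outcomes.

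At stake is the second half of the study hypothesis. The population is people with bipolar disorder, and the background argues that liraglutide may be the weight-loss drug least likely to exacerbate psychiatric symptoms. Readers will look to this trial for evidence on that, and the plan does not say what result would count as evidence.

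**Working it through.** **Plan's own figure.** Inputs from Sample Size Calculation: 56 in the modified ITT sample, so 28 per arm; two-sided 0.05; power 0.80. For a two-sample t-test with d = 0.76, the noncentrality is 0.76 / √(2/28) = 2.84 on 54 df, which gives power 0.798. The smallest d with 80% power is 0.762. The stated 0.76 reproduces. It applies to weight; there is no counterpart for a psychiatric outcome.

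**Numbers per arm for safety.** The safety population may reach 60, so 28 and 30 per arm are both shown.

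**Event proportions.** The plan gives no expected psychiatric event rate for this trial, so the placebo rates are assumptions. Power is the sum of binomial probabilities over all pairs of counts with more events on drug and a two-sided Fisher p ≤ 0.05.

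| Placebo v liraglutide | 28 per arm | 30 per arm |
|---|---|---|
| Tripling, 5% v 15% | 8% | 9% |
| Tripling, 10% v 30% | 33% | 37% |
| Tripling, 13% v 39% | 50% | 54% |
| Tripling, 15% v 45% | 61% | 64–65% |
| Tripling, 20% v 60% | 82% | 85% |
| Doubling, 10% v 20% | 8% | 10% |
| Doubling, 15% v 30% | 17% | 19% |
| Doubling, 20% v 40% | 28% | 30% |

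An uncorrected chi-square test, which the plan also allows, is more sensitive at low rates. For a tripling at 28 and 30 per arm it gives 24% and 26% from 5%, 47% and 50% from 10%, and 72% and 74% from 15%.

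The background prints placebo rates for single psychiatric events with other weight-loss drugs, between 1.8% and 5.9% where both arms are quoted for insomnia, depression/mood problems and irritability. They are not planning assumptions, but they give a scale. At 28 per arm, Fisher's test detects a tripling of 3.4% in 2.5% of trials and of 5.9% in 12%. With 28 per arm, significance needs at least 6 events v 0, 8 v 1 or 9 v 2.

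**Width of the interval for a proportion.** With equal observed rates p, the half-width is 1.96 × √(2p(1−p)/28): about 11 percentage points at 5%, 16 at 10% and 21 at 20%.

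**Symptom scales.** The SD of MADRS change is not in the documents; 4 to 9 is assumed. The half-width is t(0.975, 54) × SD × √(2/28), with t = 2.005. Power is for a true 3-point worsening, an illustrative size, using the noncentral t.

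| SD | 95% CI half-width | Power for +3 points |
|---|---|---|
| 4 | 2.1 | 79% |
| 5 | 2.7 | 60% |
| 6 | 3.2 | 45% |
| 7 | 3.7 | 35% |
| 8 | 4.3 | 28% |
| 9 | 4.8 | 23% |

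**What a margin would need.** With assumed equal true rates, one-sided 0.025 and 80% power, a 10-point margin needs 75 per arm at 5% events, 142 at 10% and 252 at 20%. A 20-point margin needs 19, 36 and 63. Only a wide margin is within reach of 28 to 30 per arm.

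**The case against.** The strongest reply is that the plan never says a non-significant safety test will be taken as proof of safety. A reader might infer that from the hypothesis wording combined with the p ≤ 0.05 rule, but no section states it, and the sentence on significance is general. That stands, and the point here does not depend on it: the tests provided cannot support a no-increase claim, whatever the authors intend.

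A reader might also infer that the trial would usually miss even a tripling of psychiatric events. That holds only for rarer events. By Fisher's test at 28 per arm, power reaches 50% at a placebo rate of about 13% and 82% at 20%. A composite of any psychiatric event over 40 weeks in bipolar disorder could lie in that range, so the claim cannot be made without a rate.

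Other parts of the reply also stand:
- The wording is a prediction, weight is the primary objective, and the sentence directly before the promise of proof is about weight. How much is to be proved is ambiguous.
- Entry requires MADRS of 19 or less and a score above 19 leads to discontinuation, so a small SD of change is plausible. This is why the range starts at 4.
- The mixed model reports a group difference for secondary outcomes. If that covers YMRS and MADRS, an estimate may already be planned, and repeated measures may sharpen it beyond the single-timepoint t-test used here.
- That adverse events will be formally tested is inferred from the general reference to categorical outcomes. If they are not tested, that part of the hypothesis has no inference rule at all.

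None of these supplies a margin, an interval or an interpretation rule.

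**Conclusion.** The concern holds as a gap between hypothesis and method. The psychiatric part of the hypothesis asserts no worsening; the analysis contains only two-sided tests of difference, with no margin, interval criterion or power for it. That mismatch is in the text and rests on no assumption.

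Its size does rest on assumptions. With uncommon events (about 10% or fewer on placebo), a non-significant Fisher result is the likelier outcome even under a tripling. At 15–20% a tripling would more often than not be found, while a doubling would still be missed in at least 70% of trials. On the MADRS, the interval would extend roughly 2 to 5 points either side of the estimate, depending on an SD the plan does not give. The primary weight analysis is unaffected.

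**What to change.** In Statistical Methods:
1. Prespecify the between-arm difference with its 95% CI for MADRS, for YMRS and for the proportion with a psychiatric adverse event, in the safety population.
2. State that a non-significant difference will not be interpreted as no worsening, and report the largest worsening that each interval does not exclude.
3. Allow a claim of no worsening only if the investigators fix a margin before unblinding and the interval excludes it. At this sample size such a margin would have to be wide, so items 1 and 2 are the core of the change.

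Reword the hypothesis in the background and in Study hypothesis (es) to match, for example as estimating the effect on psychiatric symptoms and adverse events.

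The cost is wording and a few lines of output; no new data or participants are needed. The downside is that the safety conclusion will probably become that a worsening of up to some stated size is not excluded, which is a weaker message than the present hypothesis.

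### The primary mixed model omits the antipsychotic stratum used in randomisation, and the imbalance-triggered covariate rule cannot in practice admit it and leaves the primary model dependent on the data

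*Combined protocol and SAP*

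**What the plan says.** All of this is in the combined protocol and SAP, under Statistical Methods unless noted.

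- **Why the factor was chosen.** "Antipsychotic medications used to treat BP are associated with weight gain and development of obesity". Current use of any listed antipsychotic is therefore taken ("trifluoperazine, or ziprasidone) as a stratifying factor"), with blocks of six. The expected share is "about 50%-66% of patients will also be receiving an antipsychotic drug".
- **Primary model.** "These LDA models will include variables for treatment, time, and treatment x time" is the full list of fixed effects. Random intercepts and slopes are allowed. "The statistical test for the interaction term will be the measure of a treatment effect". For percent change in weight, the week-40 difference is also reported.
- **Covariates.** The default is none: "treatment groups and generally no covariates will be used in the analyses". The exception has two steps. If a characteristic differs significantly between arms at baseline, its correlation with the outcomes is tested. If that is significant too, "then the variable will be added as a covariate to the efficacy analysis".
- **Sample Size Calculation.** With 56 analysed, "significance level of 0.05 and power of 0.80, we will be able to detect effect sizes as small as 0.76".

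Nothing exempts the stratification factor from the covariate rule or places it in a model elsewhere.

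**The concern.** The plan treats antipsychotic use as prognostic when it allocates patients and ignores it when it analyses them. Stratified allocation makes the treatment estimate more precise if the factor is prognostic. A model without the factor still counts the between-stratum variation as error. The reported standard error is then too large, the test is conservative and power is lost.

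The covariate rule looks like a safeguard but does not help here. It waits for an imbalance that the stratified blocks are designed to prevent. For every other variable it makes the content of the primary model depend on tests of observed baseline and outcome data. The documents do not list which variables will be tested.

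The form of adjustment also matters. The declared test is a comparison of slopes, so a covariate entered only as a main effect leaves the relevant variance where it was.

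**Working it through.** **1. The plan's own figure.** With 28 per arm and d = 0.76, the noncentrality is 0.76 × √(28/2) = 2.84. The noncentral t with 54 df gives power 79.8%, and the detectable d at 80% power is 0.762. The 0.76 reproduces. (60 × 0.95 = 57 against the stated 56, which is immaterial.)

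**2. Can the rule admit the stratum?** With blocks of six within strata, the arms differ by at most 3 patients in each stratum. All allocations of 60 patients with 30 to 40 users were enumerated. The most unequal is 39 users split 21 v 18, with 30 per arm:

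X² = 60 × (21 × 12 − 9 × 18)² / (39 × 21 × 30 × 30) = 486,000 / 737,100 = 0.66, p = 0.417 (smallest Fisher p 0.589).

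If every loss falls in the smallest cell of that split, p is 0.092 after four losses (the planned 56), 0.051 after five and 0.025 after six. In simulations of 8,000 trials per setting with four random losses, at shares of 0.50, 0.58 and 0.66, the trigger never fired.

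**3. What the omission costs.** The documents give no effect of antipsychotic use on weight change, so it is varied.

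- From the plan: 56 analysed, 16 post-baseline visits, SD 6 and difference 0.76 × 6 = 4.56 (given in kg, used here as outcome units).
- Assumed: 60% users, intercept SD 1.5, residual SD 1.2, and a stratum effect growing linearly to the stated difference at week 40, contained within the total SD.

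Results for the treatment-by-time test, complete data, 20,000 simulated trials per cell:

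| User/non-user difference at week 40 | 2 | 3 | 4 | 5 |
|---|---|---|---|---|
| Share of variance, 0.24 × d²/36 | 2.7% | 6.0% | 10.7% | 16.7% |
| Type I error, no stratum | 0.046 | 0.043 | 0.038 | 0.033 |
| Type I error, stratum × time | 0.050 | 0.050 | 0.050 | 0.050 |
| Power, no stratum | 82.9% | 83.2% | 83.8% | 84.7% |
| Power, stratum main effect only | 82.9% | 83.2% | 83.8% | 84.7% |
| Power, stratum × time | 83.5% | 84.9% | 86.8% | 89.2% |
| Loss (points) | 0.6 | 1.6 | 2.9 | 4.5 |

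At shares of 50% and 66%, the loss is 1.8 and 1.7 points for a difference of 3, and 4.6 and 4.6 for a difference of 5.

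*Check by formula* (intercept and slope independent). The visit weeks have mean 16 and sum of squares 2,410. The variance of a patient's fitted slope, scaled to 40 weeks, is V = 36 − 1.5² − 1.2² + 1600 × 1.2²/2410 = 33.27, of which 0.24 × d² is due to the stratum.

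- Type I error without the stratum is 2Φ(−1.96 × √(V/(V − 0.24d²))) = 0.047, 0.043, 0.037, 0.030.
- Power with stratum × time, from the noncentral t with 53 df and noncentrality 4.56 × √14/√(V − 0.24d²), is 83.8%, 85.2%, 87.0%, 89.4%.

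Both agree with the simulation.

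*Why a main effect does nothing here.* With complete data the model separates into an equation for patient intercepts and one for patient slopes. A main effect adds a regressor to the first only, so the slope estimate is unchanged. For the week-40 contrast at a difference of 5, power is 82.8% without the stratum, 83.0% with a main effect and 87.5% with stratum × time. A small REML check with an assumed 30% dropout and a difference of 4 (607 trials) gave slope-test power of 78.4%, 78.8% and 82.0%.

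*Second route.* A plain week-40 comparison with assumed R² of 0.05, 0.10 and 0.20 for the stratum gives power of 81.0%, 81.1% and 81.6% unadjusted, against 82.3%, 84.0% and 87.6% adjusted. The direction and size are similar.

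**4. How often the rule changes the model.** Assume 10 to 20 independent baseline variables.

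- First step only: 1 − 0.95¹⁰ = 40% and 1 − 0.95²⁰ = 64%.
- Both steps, no variable prognostic: 1 − (1 − 0.05²)¹⁰ = 2.5% and 1 − (1 − 0.05²)²⁰ = 4.9%.
- Both steps, every variable correlated 0.3 with the outcome (about 62% power at n = 56): 1 − (1 − 0.05 × 0.62)¹⁰ = 27% and, for 20 variables, 47%.

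**The case against.** The strongest reply is that little is lost. The plan ties antipsychotics to weight gain in general, and patients must have been on a stable regimen for three months, so a slope difference during the trial is plausible but not shown. Unadjusted power stays above 80% in every cell of the table, type I error stays at or below 0.05, and the 4.5-point loss needs a stratum difference larger than the treatment effect itself. This stands as a limit on size. It does not explain why a factor thought important enough to stratify on should be left out of the model.

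Four narrower points have some force.

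- The 40% to 64% covers only the first step of the rule. The two-step figures are the relevant ones, and they are small unless the variables are prognostic.
- The rule's inability to admit the stratum depends on blocks being formed within strata and on about the planned number of losses. Six losses in one cell could trigger it, though that pattern is very unlikely.
- The phrase about adding a covariate does not exclude an interaction with time, and the exact null result for a main effect holds only for the slope test with complete data. The plan should say which form is meant.
- Selection by AICc and the optional transformations of outcome and time also leave the model open. Removing the covariate rule does not settle those.

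**Conclusion.** The concern holds. The stratum is absent from the primary model, the rule will not bring it in at the expected 50% to 66% share, and the rule leaves the choice of other covariates to the data. The first two rest on the text and on enumeration, assuming blocks of six within strata.

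The cost is in efficiency, not validity: about 0.6 to 4.5 percentage points of power over the assumed differences of 2 to 5, and none if antipsychotic use does not predict weight change. The estimate is not biased, type I error is not inflated, and the sample size calculation stands. In a trial of 60 planned at 80% power for an effect as large as 0.76, this is an improvement worth making. It is not a defect that invalidates the analysis.

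**What to change.** Replace the covariate paragraph in Statistical Methods with text such as:

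> The primary and continuous secondary mixed models will include antipsychotic use at randomisation (yes/no) and its interaction with the same time variable used in treatment × time. For percent change in weight, baseline weight and its interaction with time will also be included. The LOCF change-score comparisons will be adjusted for the same stratum and the baseline value; where a rank test is used, it will be stratified by antipsychotic use (van Elteren test). No covariate will be selected by baseline significance tests; baseline characteristics will be described only.

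The stratum and stratum-by-time terms are the essential part. The baseline-weight terms are secondary: their benefit has not been quantified, and percent change already scales by baseline weight. The comparison of proportions losing at least 5% is not covered by this text, and the sponsor may wish to stratify it in the same way.

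The cost is SAP wording, agreed before unblinding, and a few degrees of freedom. Both variables are already collected.
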